### **7.1.2.4 Adverse Event Monitoring**

Please refer to Section 7.2 – Assessing and Recording Adverse Events for details regarding assessment and documentation of AEs. Laboratory AEs will be based on safety laboratory test results, including hematology and chemistry tests from blood and urinalysis from urine. All AEs should be documented on the appropriate eCRF. Refer to Section 7.1.3 – Laboratory Procedures/Assessments and Section 6.0 – Trial Flow Chart for more details on types of tests and timing of collection.

### **7.1.2.5 Local Tolerability Monitoring**

Local infusion site tolerability will be evaluated at the time points specified in Section 6.0 – Trial Flow Chart. The tolerability of all study therapy at the local IV infusion site will be based on investigator inspection and, when applicable, subject comments regarding signs and symptoms of intolerance. The IV infusion site should be observed to determine the presence/absence of erythema, induration, pain, tenderness, warmth, swelling, ulceration, local phlebitis, rash, or other reactions.

### **7.1.3 Laboratory Procedures/Assessments**

Details regarding specific laboratory procedures/assessments to be performed in this trial are provided below. The total amount of blood to be drawn over the course of the trial (from pre-trial to post-trial visits), including approximate blood volumes drawn by visit and by sample type per subject, can be found in Appendix 12.2 – Approximate Blood/Tissue Volumes Drawn/Collected by Trial Visit and by Sample Types.

#### **7.1.3.1 Laboratory Safety Evaluations (Hematology, Chemistry, and Urinalysis)**

Laboratory tests for hematology, chemistry and urinalysis are specified in [Table 3](#).

Clinically stable renal function, as measured by creatinine clearance (see Appendix 12.3), is an inclusion criterion for this trial. In addition to values obtained from scheduled chemistry blood draws during the study, the serum creatinine values used to calculate creatinine clearance for eligibility determination will also be recorded on the appropriate eCRF.

Urine will be collected from subjects who are either toilet trained and able to provide a specimen, catheterized, or fitted with a urine collection bag.

Table 3 Laboratory Tests

Hematology	Chemistry	Urinalysis	Other
Hematocrit	Albumin	Blood	Serum $\beta$ -hCG a
Hemoglobin	Alkaline phosphatase	Glucose	
Platelet count	ALT	Protein	
WBC count (total and differential)	AST	Specific gravity	
Neutrophils (% absolute)	Bicarbonate	Microscopic exam, if abnormal results are noted	
Band neutrophils (% absolute)	Calcium	pH	
Lymphocytes (% absolute)	Carbon dioxide		
Eosinophils (% absolute)	Chloride		
Basophils (%)	Creatinine		
	Glucose		
	Phosphorus		
	Potassium		
	Sodium		
	Total bilirubin		
	Direct and indirect bilirubin, if total bilirubin is elevated above the ULN		
	Total protein		
	Blood urea nitrogen		

Abbreviations: ALT: alanine aminotransferase; AST: aspartate aminotransferase;  $\beta$ -hCG:  $\beta$ -human chorionic gonadotropin; ULN: upper limit of normal; WBC: white blood cell.

a. Female subjects of child-bearing potential only.

### 7.1.3.2 Pharmacokinetic/Pharmacodynamic Evaluations

Four PK samples per subject will be collected in each of the age cohorts as follows:

1. First PK sample: predose sample taken within 30 minutes before the start of study drug infusion.
2. Second PK sample: collected within 10 minutes after the end of study drug infusion.
3. Third PK sample:
  - Cohorts 1 through 4: obtained 1.5 to 2.5 hours after the start of study drug infusion.
  - Cohort 5: obtained 2 to 5 hours after the start of study drug infusion.

4. Fourth PK sample:

- Cohorts 1 through 4: obtained 4.5 to 6 hours after the start of study drug infusion.
- Cohort 5: obtained 6 to 12 hours after the start of study drug infusion.

All PK samples must be drawn within the specified time windows, and the actual sampling times must be documented. This sampling scheme allows for a balance between the maximum coverage of the concentration profile across time required to adequately characterize the PK profile, while maintaining a minimal number of samples per subject.

The following model-based and derived PK parameters will be calculated for REL and/or imipenem, as appropriate:

- $AUC_{0-\infty}$
- $C_{max}$
- %TMIC (imipenem only)
- Systemic clearance (CL)
- Central volume of distribution ( $V_c$ )

The following noncompartmental analysis (NCA)-based PK parameters will be calculated for cilastatin:

- $AUC_{0-\infty}$
- Time to maximum observed plasma drug concentration
- Concentration at end of infusion (CEOI)
- $t_{1/2}$
- CL
- Volume of distribution ( $V_{ss}$ )

#### **7.1.3.2.1 Blood Collection for Plasma MK-7655A**

Sample collection, storage, and shipment instructions for plasma samples will be provided in the operations/laboratory manual.

The method of collection for PK samples is at the discretion of the investigator (eg, peripherally inserted central catheter line, indwelling catheter access, individual peripheral phlebotomies, peri-operatively placed arterial line). A separate IV line for PK sample collection is highly recommended; if a separate IV line is not clinically feasible, refer to the operations/laboratory manual for further details of allowable alternative collection methods.

## **7.1.4 Other Procedures**

### **7.1.4.1 Withdrawal/Discontinuation**

Subjects who discontinue treatment prior to completion of the treatment regimen (ie, discontinuation of study drug partway through the infusion) should be encouraged to continue to be followed for all remaining study visits.

When a subject discontinues/withdraws from participation in the trial, all applicable activities scheduled for the early withdrawal trial visit, as specified in Section 6.0 – Trial Flow Chart, should be performed at the time of discontinuation. Any adverse events which are present at the time of discontinuation/withdrawal should be followed in accordance with the safety requirements outlined in Section 7.2 - Assessing and Recording Adverse Events.

### **7.1.4.2 Subject Blinding/Unblinding**

This is an open label trial; there is no blinding for this trial.

### **7.1.4.3 Domiciling**

In order to participate in this study, subjects must be hospitalized and expected to remain hospitalized until at least 24 hours after completion of study drug administration.

### **7.1.4.4 Calibration of Equipment**

The investigator or qualified designee has the responsibility to ensure that any device or instrument used for a clinical evaluation/test during a clinical study that provides information about inclusion/exclusion criteria and/or safety or efficacy parameters shall be suitably calibrated and/or maintained to ensure that the data obtained is reliable and/or reproducible. Documentation of equipment calibration must be retained as source documentation at the study site.

## **7.1.5 Visit Requirements**

Visit requirements are outlined in Section 6.0 - Trial Flow Chart. Specific procedure-related details are provided above in Section 7.1 - Trial Procedures.

### **7.1.5.1 Screening**

Within 48 hours prior to the start of study drug infusion, potential subjects will be evaluated to determine that they fulfill the entry requirements as set forth in Section 5.1 – Entry Criteria. Screening procedures may be repeated after consultation with the Sponsor. If the subject is rescreened, screening procedures should be repeated, unless they fall within the window specified.

### **7.1.5.2 Treatment Period**

Details regarding procedures, assessments, and scheduling windows for the single treatment visit (ie, Visit 2) are presented in Section 6.0 – Trial Flow Chart. Notably, blood samples for plasma PK assessments and vital sign measurements will be collected several times at Visit 2 (see Section 6.0 – Trial Flow Chart for further details).

### **7.1.5.3 Discontinued Subjects Continuing to be Monitored in the Trial**

Subjects that discontinue treatment (ie, subjects that discontinue from study drug partway through the infusion) or who withdraw from the trial at any point after the start of study drug infusion should have all safety assessments, including clinical safety laboratory assessments, vital sign measurements, directed physical examination, collection of AEs and concomitant medications, and local tolerability monitoring (for subjects who discontinue from treatment or withdraw from the trial between the start of study drug infusion and the Day 2 visit) completed as per Section 6.0 – Trial Flow Chart, but do not need to have PK sampling performed.

Subjects that withdraw from the trial prior to receiving a dose of study drug (eg, due to removal of consent by the parent or LAR, or due to an emergent condition or circumstance which, in the opinion of the investigator or Sponsor, places the subject at unnecessary risk through continued participation, or does not allow adherence to the protocol) do not need to undergo further visits or assessments.

### **7.1.5.4 Post-Trial**

Subjects will be required to either return to the study site or have a telephone contact approximately 14 days after the single dose of study drug for a concomitant medication review and AE monitoring.

## **7.2 Assessing and Recording Adverse Events**

An adverse event is defined as any untoward medical occurrence in a patient or clinical investigation subject administered a pharmaceutical product and which does not necessarily have to have a causal relationship with this treatment. An adverse event can therefore be any unfavourable and unintended sign (including an abnormal laboratory finding, for example), symptom, or disease temporally associated with the use of a medicinal product or protocol-specified procedure, whether or not considered related to the medicinal product or protocol-specified procedure. Any worsening (i.e., any clinically significant adverse change in frequency and/or intensity) of a preexisting condition that is temporally associated with the use of the Sponsor's product, is also an adverse event.

Changes resulting from normal growth and development that do not vary significantly in frequency or severity from expected levels are not to be considered adverse events. Examples of this may include, but are not limited to, teething, typical crying in infants and children and onset of menses or menopause occurring at a physiologically appropriate time.

Sponsor's product includes any pharmaceutical product, biological product, device, diagnostic agent or protocol-specified procedure, whether investigational (including placebo

or active comparator medication) or marketed, manufactured by, licensed by, provided by or distributed by the Sponsor for human use.

Adverse events may occur during clinical trials, or as prescribed in clinical practice, from overdose (whether accidental or intentional), from abuse and from withdrawal.

All adverse events that occur after the consent form is signed but before treatment allocation/randomization must be reported by the investigator if they cause the subject to be excluded from the trial, or are the result of a protocol-specified intervention, including but not limited to washout or discontinuation of usual therapy, diet, placebo treatment or a procedure. From the time of treatment allocation/randomization through 14 days following cessation of treatment, all adverse events must be reported by the investigator. Such events will be recorded at each examination on the Adverse Event case report forms/worksheets. The reporting timeframe for adverse events meeting any serious criteria is described in section 7.2.3.1. The investigator will make every attempt to follow all subjects with non-serious adverse events for outcome.

Electronic reporting procedures can be found in the Electronic Data Capture (EDC) data entry guidelines. Paper reporting procedures can be found in the Investigator Trial File Binder (or equivalent).

### **7.2.1 Definition of an Overdose for This Protocol and Reporting of Overdose to the Sponsor**

In this trial, an overdose is any dose higher than 10% of the calculated age-appropriate dose specified in Section 5.2.1.1 – Dose Selection (Preparation) or in subsequent Protocol Clarification Letters.

If an adverse event(s) is associated with (“results from”) the overdose of Sponsor's product or vaccine, the adverse event(s) is reported as a non-serious adverse event, unless other serious criteria are met.

If a dose of Sponsor's product or vaccine meeting the protocol definition of overdose is taken without any associated clinical symptoms or abnormal laboratory results, the overdose is reported as a non-serious adverse event, using the terminology “accidental or intentional overdose without adverse effect.”

All reports of overdose with and without an adverse event must be reported by the investigator within 24 hours to the Sponsor either by electronic media or paper. Electronic reporting procedures can be found in the EDC data entry guidelines. Paper reporting procedures can be found in the Investigator Trial File Binder (or equivalent).

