### 5.2.1 Dose Selection/Modification

#### 5.2.1.1 Dose Selection (Preparation)

[Table 2](#) displays the proposed initial doses of the study drug for each age cohort. The proposed initial doses may be modified as described in Section 5.2.1.2 – Dose Modification. The dose modifications for Cohorts 1 through 4 that occurred as a result of the first interim review in these cohorts (ie, after 50% enrollment; see Section 8.7) are described in Section 5.2.1.2.1, along with the results of the second interim review (ie, following completion of enrollment in Cohorts 1 through 3) that led to the initial doses for Cohorts 4 and 5.

Table 2 Imipenem/Cilastatin/Relebactam (IMI/REL) Doses by Age Cohort

Age Cohort	Age Range	IMI/REL Proposed Initial Dose a
1 (n=6)	12 to <18 years	15/7.5 mg/kg over 30 min
2 (n=6)	6 to <12 years	15/7.5 mg/kg over 30 min
3 (n=6)	2 to <6 years	15/7.5 mg/kg over 30 min
4 (n=8)	3 months to <2 years b	10/5 mg/kg over 60 min c
5 (n=18)	Birth to <3 months d	10/5 mg/kg over 60 min c

Abbreviations: IMI/REL: imipenem/cilastatin/relebactam; TBD: to be determined

a The proposed initial doses may be modified based on interim data as described in Section 5.2.1.2 – Dose Modification. The dose modifications for Cohorts 1 through 4 that occurred as a result of the first interim review in these cohorts are described in Section 5.2.1.2.1. Single IV doses for all cohorts will not exceed the adult maximum dose of 500 mg IMI and 250 mg REL.

b At least 4 subjects in Cohort 4 will be <1 year of age.

c Initial doses of IMI/REL for subjects in Cohorts 4 and 5 were selected based on PK modeling and simulation analyses, after incorporating observed PK data from Cohorts 1 through 3 (Section 5.2.1.2.1). Initial doses for Cohorts 4 and 5 were communicated to sites via a Protocol Clarification Letter.

d Cohort 5 will be further subdivided into the following 3 age subcohorts:

- 4 weeks to <3 months of age; at least 6 subjects
- 1 to <4 weeks of age; at least 6 subjects
- <1 week of age; at least 6 subjects

The rationale for selection of doses to be used in this trial is provided in Section 4.0 – Background & Rationale. Additional details for preparation and administration of study drug are provided in a separate Pharmacy Manual.

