### 5.2.1.2 Dose Modification

The goal of this trial is to determine doses of IMI/REL for each pediatric age cohort that achieve similar therapeutic exposure parameters as seen in clinical trials in adults and have an acceptable safety profile. As such, all observed PK data will be entered into a rolling population PK model-based simulation. For each age cohort, the Sponsor will assess dose suitability during the planned interim reviews based on the observed PK and safety data from the first half of subjects enrolled into the cohort. The following parameters will be considered in determination of pediatric doses:

- Simulated population PK parameters for each age cohort approach the following values, as expected in adults:
  - Single-dose REL exposure of  $AUC_{0-\infty} \geq 37.5 \mu\text{M}\cdot\text{hr}$  (and  $\leq 200 \mu\text{M}\cdot\text{hr}$ ). Doses associated with this exposure have been established as being well tolerated in adults.
  - $\geq 30\%$  TMIC (within proposed dosing interval) for single-dose imipenem (and  $AUC_{0-\infty} \leq 250 \mu\text{M}\cdot\text{hr}$ ). Doses achieving these targets have been established as safe and efficacious in adults.

- Observed safety data demonstrates an acceptable safety profile, as defined by no life-threatening toxicities considered by the investigator to be related to study treatment. Life-threatening toxicities are defined as follows:
  - For laboratory AEs, a grade of 4 on the Division of Microbiology and Infectious Diseases pediatric toxicity scale [12].
  - For clinical AEs, events that are considered serious due to being life-threatening, as defined in Section 7.2.4 – Evaluating Adverse Events and as documented on the electronic case report form (eCRF).

Modified doses will not exceed the adult maximum of 500 mg IMI and 250 mg REL for a single IV dose, and dose modifications, if required, will be communicated to sites via Protocol Clarification Letters.

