### **7.2.3 Immediate Reporting of Adverse Events to the Sponsor**

#### **7.2.3.1 Serious Adverse Events**

A serious adverse event is any adverse event occurring at any dose or during any use of Sponsor's product that:

- Results in death;
- Is life threatening;
- Results in persistent or significant disability/incapacity;
- Results in or prolongs an existing inpatient hospitalization;
- Is a congenital anomaly/birth defect;
- Is an other important medical event.

**Note:** In addition to the above criteria, adverse events meeting either of the below criteria, although not serious per ICH definition, are reportable to the Sponsor in the same timeframe as SAEs to meet certain local requirements.

- Is a cancer;
- Is associated with an overdose.

Refer to [Table 4](#) for additional details regarding each of the above criteria.

For the time period beginning when the consent form is signed until treatment allocation/randomization, any serious adverse event, or follow up to a serious adverse event, including death due to any cause, that occurs to any subject must be reported within 24 hours to the Sponsor if it causes the subject to be excluded from the trial, or is the result of a protocol-specified intervention, including but not limited to washout or discontinuation of usual therapy, diet, placebo treatment or a procedure.

For the time period beginning at treatment allocation/randomization through 14 days following cessation of treatment, any serious adverse event, or follow up to a serious adverse event, including death due to any cause, whether or not related to the Sponsor's product, must be reported within 24 hours to the Sponsor either by electronic media or paper. Electronic reporting procedures can be found in the EDC data entry guidelines. Paper reporting procedures can be found in the Investigator Trial File Binder (or equivalent).

Additionally, any serious adverse event, considered by an investigator who is a qualified physician to be related to the Sponsor's product that is brought to the attention of the investigator at any time outside of the time period specified in the previous paragraph also must be reported immediately to the Sponsor.

All subjects with serious adverse events must be followed up for outcome.

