### **7.2.4 Evaluating Adverse Events**

An investigator who is a qualified physician will evaluate all adverse events with respect to the elements outlined in [Table 4](#). The investigator's assessment of causality is required for each adverse event. Refer to [Table 4](#) for instructions in evaluating adverse events.

Table 4 Evaluating Adverse Events

Maximum Intensity	Mild	awareness of sign or symptom, but easily tolerated (for pediatric trials, awareness of symptom, but easily tolerated)
	Moderate	discomfort enough to cause interference with usual activity (for pediatric trials, definitely acting like something is wrong)
	Severe	incapacitating with inability to work or do usual activity (for pediatric trials, extremely distressed or unable to do usual activities)
Seriousness	A serious adverse event (AE) is any adverse event occurring at any dose or during any use of Sponsor's product that:	
	† Results in death ; or	
	† Is life threatening ; or places the subject, in the view of the investigator, at immediate risk of death from the event as it occurred [Note: This does not include an adverse event that, had it occurred in a more severe form, might have caused death.]; or	
	† Results in a persistent or significant disability/incapacity (substantial disruption of one's ability to conduct normal life functions); or	
	† Results in or prolongs an existing inpatient hospitalization (hospitalization is defined as an inpatient admission, regardless of length of stay, even if the hospitalization is a precautionary measure for continued observation. (Note: Hospitalization for an elective procedure to treat a pre-existing condition that has not worsened is not a serious adverse event. A pre-existing condition is a clinical condition that is diagnosed prior to the use of a Merck product and is documented in the patient's medical history.); or	
	† Is a congenital anomaly/birth defect (in offspring of subject taking the product regardless of time to diagnosis); or	
	Is a cancer (although not serious per ICH definition, is reportable to the Sponsor within 24 hours to meet certain local requirements); or	
	Overdose, although not serious per ICH definition, whether accidental or intentional, with or without an accompanying adverse event/serious adverse event, is reportable to the Sponsor within 24 hours to meet certain local requirements.	

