No, there is not a reasonable possibility of Sponsor's product relationship	Subject did not receive the Sponsor's product OR temporal sequence of the AE onset relative to administration of the Sponsor's product is not reasonable OR the AE is more likely explained by another cause than the Sponsor's product. (Also entered for a subject with overdose without an associated AE.)	

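### Section 7.2.1 sets the overdose threshold at 10% of the calculated dose, so a correctly given dose meets the definition of an overdose

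*Combined protocol and SAP*

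**What the plan says.** Section 7.2.1 gives the protocol's only definition of overdose: "an overdose is any dose higher than 10% of the calculated age-appropriate dose specified in Section 5.2.1.1" or in later Protocol Clarification Letters. Three duties follow from it.

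- **Expedited reporting.** "All reports of overdose with and without an adverse event must be reported by the investigator within 24 hours to the Sponsor" (Section 7.2.1). Table 4 in Section 7.2.4 repeats this for an overdose "with or without an accompanying adverse event/serious adverse event, is reportable to the Sponsor within 24 hours to meet certain local requirements".
- **AE coding.** If the dose is "taken without any associated clinical symptoms or abnormal laboratory results, the overdose is reported as a non-serious adverse event" (Section 7.2.1), under a fixed term for an overdose that caused no adverse effect.
- **SAE timeframe for linked events.** Section 7.2.3.1 puts an adverse event on the SAE reporting clock if it "Is associated with an overdose".

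The reference doses are in Table 2 of Section 5.2.1.1. For Cohort 5 the initial dose is "10/5 mg/kg over 60 min". Section 8.6.2 tabulates, by age cohort and dose level, the percentages of subjects with any AE, a drug-related AE, an SAE and a drug-related SAE, together with the individual AEs.

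**The concern.** Ten percent of a dose is 0.10 times that dose. A definition built on that threshold labels the protocol's own dose an overdose, along with any partial infusion that gets past one tenth of it. The evident intention is a margin of 10% above the calculated dose, that is, 1.10 times it.

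This is an operative reporting rule, so the wording matters more than a slip in background text would. A site that followed it to the letter would file a 24-hour report for every fully dosed subject and record an overdose AE for each symptom-free one. The any-AE percentage would then tell the reader nothing about tolerability. A site that silently corrects the sentence has to guess the margin, because no other section states it.

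**Working it through.** **Inputs.** The threshold is from Section 7.2.1. The doses (15/7.5 mg/kg for Cohorts 1 to 3 and 10/5 mg/kg for Cohorts 4 and 5 initially) and the 500/250 mg cap are from Table 2. The 60 (±5)-minute infusion for Cohort 5 is from Section 5.2.2. The plan derives no figure here, so there is none to reproduce.

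**Formulas.** With D the calculated dose, the literal rule is dose > 0.10 × D. The evident intended rule is dose > 1.10 × D.

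| Calculated dose D (imipenem/relebactam) | Literal: above 0.10 × D | Evident intent: above 1.10 × D |
|---|---|---|
| 15/7.5 mg/kg | 1.5/0.75 mg/kg | 16.5/8.25 mg/kg |
| 10/5 mg/kg | 1/0.5 mg/kg | 11/5.5 mg/kg |
| 500/250 mg (cap) | 50/25 mg | 550/275 mg |

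The ratio of the two thresholds is 1.10 / 0.10 = 11 in every row. A correct full dose (1.00 × D) exceeds the literal threshold and does not exceed the intended one.

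**Illustration for Cohort 5.** Assume a 3 kg neonate; the weight is my assumption. The assigned dose is 3 × 10/5 = 30/15 mg. The literal threshold is 0.10 × 30/15 = 3/1.5 mg, and the intended one is 1.10 × 30/15 = 33/16.5 mg. At a constant infusion rate (also assumed), the literal threshold is passed after 0.10 × 60 = 6 minutes, with a range of 5.5 to 6.5 minutes for infusions of 55 to 65 minutes.

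**Does another section supply the threshold?** No. Section 7.2.3.1 and Table 4 repeat the reporting duty and give no number. The Summary of Changes for Amendment 2 does not list Section 7.2.1.

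**What a literal reading would change in the tables.**

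- *Any AE:* every fully dosed subject has either symptoms or an overdose entry, so the rate is 100%. The individual overdose term also appears in the listing of AEs.
- *Drug-related AE and drug-related SAE:* unchanged. In Table 4 the no-relationship category is "Also entered for a subject with overdose without an associated AE".
- *SAE:* unchanged, because Section 7.2.1 classes the symptom-free overdose as non-serious.
- *Dose decisions:* unchanged. The safety criterion in Section 5.2.1.2 is "no life-threatening toxicities considered by the investigator to be related to study treatment", and a non-serious, unrelated entry does not touch it.
- *Pharmacokinetic results:* unchanged, since they do not depend on AE coding.

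**The case against.** The strongest reply is that nobody would read the sentence literally. A definition that makes the assigned dose an overdose contradicts the word it defines, and Section 7.2 describes an adverse event as something untoward, which a per-protocol infusion is not. Section 5.8.1 also treats a partly given infusion as a treatment discontinuation.

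The error is also one-sided. Any dose above 1.10 × D is above 0.10 × D, so a true overdose is always caught. The only doses left out are those at or below one tenth of the dose, which are not overdoses. A mistaken report would reach the sponsor within 24 hours and expose the problem. The overdose entries would carry one fixed term and could be separated in the AE tables.

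All of this stands, and it keeps the point minor. It does not make the sentence correct. The 10%-above rule remains an inference, and sites should not have to infer a margin that triggers expedited reporting.

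**Conclusion.** The concern holds as a wording error of low severity. The literal threshold is 11 times lower than the evident one, and it captures every correctly given dose. The worst case is over-reporting and a 100% any-AE rate; this is an upper bound under literal application, not an expected outcome, and the documents give no sign that it occurred. Detection of true overdoses, dose decisions and the primary pharmacokinetic analysis are unaffected.

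The conclusion rests on two conditions. The intended rule is inferred. The figure of 11/5.5 mg/kg holds while the Cohort 5 dose stays at 10/5 mg/kg, which the Cohort 5 interim review may change. Section 5.2.1.2.1 reports that Cohorts 1 to 4 are fully enrolled, so corrected wording can apply prospectively only to Cohort 5, planned at 18 subjects in Table 2. The documents do not say how many of these remain to be dosed.

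**What to change.** Reword the sentence in Section 7.2.1 along these lines: *an overdose is a dose that exceeds the calculated age-appropriate dose (Section 5.2.1.1 or later Protocol Clarification Letters) by more than 10%.* At the Cohort 5 dose this means above 11/5.5 mg/kg. The sponsor should confirm that 10% is the margin it intended.

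The cost is one phrase in the next amendment or in a Protocol Clarification Letter. The protocol describes such letters for doses and infusion durations, so the sponsor should decide whether a safety definition can go out that way or needs an amendment with ethics review. Dosing, pharmacokinetic analysis, interim reviews and sample size do not change.
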